## 13.2.6 Simulations

Simulations will be conducted using the final model to predict long-term buprenorphine plasma exposure after stopping SUBLOCADE treatment (6 injections of 300 mg or 2 injections of 300 mg followed by 4 injections of 100 mg).

The distribution of predicted buprenorphine plasma concentrations will be summarized at each month over at least 36 months post last SUBLOCADE injection in the simulation

study. The percentage of subjects predicted to fall below the limit of quantification will be calculated at each month. Also, the distribution of times during which buprenorphine plasma concentrations stay above the lower limit of quantification following the last dose of SUBLOCADE will be provided.

Additional simulation studies may be conducted as needed.

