### 1.2 Clinical Pharmacology Information

After SUBLOCADE injection in clinical studies, an initial buprenorphine peak was observed at approximately 24 hours post-dose. The initial peak was followed by a decline in plasma concentrations to a plateau throughout the monthly dosing interval, consistent with the slow release of buprenorphine from the SC depot. The apparent terminal plasma half-life of buprenorphine following SC injection of SUBLOCADE ranged between 43 to 60 days. Steady-state was achieved at 4 to 6 months following repeated monthly SC injections.

Buprenorphine is metabolized to its major metabolite, norbuprenorphine, primarily by cytochrome P450 3A4 and, to a lesser extent, by cytochrome P450 2C8. Norbuprenorphine can further undergo glucuronidation. Norbuprenorphine has been found to bind to mu-opioid receptors *in vitro*; however, norbuprenorphine is expected to have negligible contribution to brain mu-opioid receptor occupancy given its limited ability to cross the blood-brain barrier ([Ohtani 2007](#)) and has not been studied clinically for opioid-like activity. Norbuprenorphine steady-state plasma concentrations in humans after SC injection of SUBLOCADE were low compared with buprenorphine. The ratio of norbuprenorphine/buprenorphine areas under the plasma concentration-time curve (AUC) in a repeat-dose study (RB-US-12-0005) was 0.2 to 0.4, i.e., much lower than for transmucosal buprenorphine (ratio of 1.3-3.2 in the same study) due to the lack of first-pass effect.

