### **5.2 Inclusion Criteria**

#### Part A

Each individual must meet the following criteria to be enrolled in Part A of this study:

1. The subject participated in Study RB-US-13-0003 or both Studies RB-US-13-0003 and INDV-6000-301 and received at least 2 SC injections of SUBLOCADE.
2. The subject must be within 12 to 36 months post his or her last SUBLOCADE injection at the time of the Screening visit.
3. Female individuals of childbearing potential (defined as all women who were not surgically sterile or postmenopausal for at least 1 year prior to informed consent) must agree to have a pregnancy test administered prior to enrolment and throughout the study. Pregnancy will not prohibit them from participation in the study.
4. The subject must be willing to adhere to study procedures and provide written informed consent prior to the start of any study procedures.

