**Table 1 Estimates of Previous Population Pharmacokinetic Model (Combined Analysis of Phase II/III Data)**

Parameter	Description	Estimate (RSE%)		Variance (RSE%)		IIV (%)
k14	Sublingual absorption rate constant (h  )	1.17	(FIXED)	0.190	(FIXED)	45.7
k24	Fast absorption rate constant from SC depot (h  )	0.0276	(5.1)	0.654	(16)	96.1
k36	Slow absorption rate constant from SC depot (h  )	0.00362	(7.4)	1.54	(11)	191
k64	Rate constant from Transit compartment to Central (h  )	0.000510	(3.7)	0.432	(11)	73.5
CL	SUBLOCADE apparent elimination clearance (L/h)	52.0	(1.5)	0.0871	(9.5)	30.2
V4	SUBLOCADE apparent volume of central compartment (L)	433	(27)	0.647	(12)	95.4
Q	SUBLOCADE apparent distribution clearance (L/h)	79.5	(FIXED)	0.334	(FIXED)	63.0
V5	SUBLOCADE apparent volume of peripheral compartment (L)	1110	(FIXED)	0.941	(FIXED)	125
F1	Relative bioavailability of SUBUTEX compared to SUBLOCADE	0.185	(FIXED)	0.195	(FIXED)	46.4
F2	Fraction of SUBLOCADE dose absorbed by fast process	0.0679	(2.2)	0.204	(11)	NA #
FRK14	Relative change in k14 for SUBUXONE compared to SUBUTEX	0.650	(11)	NA		NA
FRF1	Relative change in F1 for SUBUXONE compared to SUBUTEX	1.47	(3.5)	NA		NA
F1DOSE	Relative change in F1 for dose ≥ 16mg compared to dose < 16mg	0.765	(FIXED)	NA		NA
θ BMI (CL)	Power coefficient for BMI on CL/F	-0.364	(21)	NA		NA
θ BMI (k24)	Power coefficient for BMI on k24	-1.32	(14)	NA		NA
θ SEX (k36)	Fractional increase in k36 for females	0.0313	(282)	NA		NA
Add	Additive residual error (ng/mL)	0.0373	(14)	NA		NA
Prop	Proportional residual error	0.190	(0.66)	NA		NA

IIV=interindividual variability calculated as  $100 \times \sqrt{\exp(\omega^2) - 1}$ , where  $\omega^2$  is the variance of related subject-specific random effect; NA=not applicable; RSE=relative standard error; # logit-normal distribution.

Source: INDV-6000-M05 Table 5

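### The planned simulations cover 6-injection courses only, yet the upper tail of time above LLOQ depends on treatment length, in both directions

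*SAP*

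**What the plan says.** SAP Section 13.2.6 names two simulated courses, both of 6 injections: "6 injections of 300 mg or 2 injections of 300 mg followed by 4 injections of 100 mg". From them it will summarise predicted concentrations and the percentage of subjects below the LLOQ month by month, over at least 36 months. It adds that "the distribution of times during which buprenorphine plasma concentrations stay above the lower limit of quantification following the last dose of SUBLOCADE will be provided". The section ends with "Additional simulation studies may be conducted as needed", which names no course and no treatment length.

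Protocol Section 14.5 speaks of the 2 dosing regimens without giving a number of injections. Protocol Section 5.2 sets the entry condition: "The subject participated in Study RB-US-13-0003 or both Studies RB-US-13-0003 and INDV-6000-301 and received at least 2 SC injections of SUBLOCADE". That is a minimum, with no maximum. The guidance that the study is meant to inform (Protocol Section 1.3) concerns exposure after stopping treatment and is not limited by how long treatment lasted.

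The SAP gives no reason for choosing 6. The nearest support is Protocol Section 1.2: "Steady-state was achieved at 4 to 6 months following repeated monthly SC injections".

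**The concern.** If every patient were near steady state after 6 injections, further injections would barely change the washout and one course length would do. That is roughly so for a typical patient. It is not so for patients with slow depot release, for whom each further injection still adds drug to the depot.

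Those same patients determine the late percentiles of time above LLOQ. A single simulated course length therefore fixes the upper tail at a value that suits neither shorter nor longer courses, in a study whose purpose is to say how long buprenorphine stays measurable. Without a label, a 95th percentile computed for 6 injections could be applied to someone who had 2, or to someone treated much longer.

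**Working it through.** **Inputs from SAP Table 1.** k64 ("Rate constant from Transit compartment to Central") is 0.000510 per h, variance 0.432. k36 ("Slow absorption rate constant from SC depot") is 0.00362 per h, variance 1.54. Apparent clearance CL is 52.0 L/h, variance 0.0871. The fast fraction F2 is 0.0679, logit-normal with variance 0.204.

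**Assumptions.** Dosing every 28 days; plasma LLOQ of 0.02, 0.05 or 0.1 ng/mL; courses of 12 and 24 injections as illustrations; the 300/100 mg regimen extended at 100 mg.

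**The plan's own figures.** The typical slow-release half-life is ln 2 / 0.000510 / 24 = 56.6 days, inside the 43 to 60 days of Protocol Section 1.2. After 6 injections the typical patient is at 1 − 2^(−168/56.6) = 87% of steady state. Half-lives of 43 and 60 days give 93% and 86%. The stated 4 to 6 months is thus reasonable for a typical patient.

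**A slow releaser, by hand.** The 5th percentile of k64 is 0.000510 × exp(−1.645 × √0.432) = 0.000173 per h, a half-life of 167 days. The fraction of steady state after n injections is 1 − 2^(−28n/167): 21% at n = 2, 50% at 6, 75% at 12 and 94% at 24. In the late phase, the change in time above any fixed limit is the half-life × log2 of the ratio of these fractions:

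- 6 to 12 injections: 167 × log2(0.752/0.502) = 97 days, about 3.2 months.
- 6 to 24 injections: 167 × log2(0.939/0.502) = 151 days, about 5.0 months.
- 2 to 6 injections: 167 × log2(0.502/0.207) = 213 days, about 7.0 months.

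At the typical half-life of 56.6 days, going from 6 to 24 injections adds only about 11 days.

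**The population.** I simulated 20,000 virtual subjects from Table 1, without covariates, random-effect correlations or residual error. The late concentration is the sum over doses of dose × (1 − F2) × k36·k64/(k36 − k64) × (exp(−k64·t) − exp(−k36·t)) / CL, where t is the time since that dose. The 95th percentile of time above LLOQ, in months on a half-month grid, is:

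| Course | LLOQ 0.02 | LLOQ 0.05 | LLOQ 0.1 |
|---|---|---|---|
| 2 × 300 mg | 37.5 | 30 | 24.5 |
| 6 × 300 mg (planned) | 44.5 | 37.5 | 31.5 |
| 12 × 300 mg | 48 | 40.5 | 35 |
| 24 × 300 mg | 50 | 42.5 | 37 |
| 2 × 300 + 4 × 100 mg (planned) | 39 | 31.5 | 26 |
| 2 × 300 + 10 × 100 mg | 40.5 | 33 | 27 |
| 2 × 300 + 22 × 100 mg | 41 | 34 | 28 |

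At LLOQ 0.05 the 300 mg median is 13.5 months after 2 injections, 15 after 6 and 15.5 after 12 or 24. The 300/100 mg median stays at 12.5 from 6 to 24 injections. The share of 300 mg subjects still at or above 0.05 ng/mL at month 36 is 2.2%, 5.8%, 7.6% and 8.6% after 2, 6, 12 and 24 injections.

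**Sensitivity.** With the full two-compartment disposition, the 300 mg 95th percentile at LLOQ 0.05 is 38.0, 41.4 and 43.4 months after 6, 12 and 24 injections. The gain from 6 to 24 is 5.2 to 5.4 months across the three LLOQs, and 2.2 months for 300/100 mg. A 30-day interval changes the gains by at most about 0.3 month. The LLOQ shifts the level of the tail but hardly changes the gain.

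**The case against.** There is a fair case for leaving the section alone. The SAP states its scenario openly, and the percentiles will be correct for that course. Six injections is a sensible reference in view of the steady-state statement in Protocol Section 1.2. The output is exploratory: the primary endpoint (Protocol Section 3) is a plot of observed concentrations and is untouched. The dosing information in the NONMEM file (SAP Section 13.2.2) lets model fitting use each subject's own history. The closing sentence of Section 13.2.6 allows further runs. The size is also no larger than other uncertainties: moving only the k64 variance by twice its stated 11% relative standard error shifts the 6-injection 95th percentile between about 34 and 40.5 months at LLOQ 0.05.

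Most of this stands, and it limits the point to the upper tail and to reporting. Two parts do not settle it. Permission to run more simulations is not a commitment to any treatment length. And parameter uncertainty does not remove the dependence on course length, which has a known direction and can be shown at little cost.

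A reader might infer that the planned simulations miss much of the exposure that the study samples. The documents do not support that. They report no distribution of injections received, and the absence of a ceiling does not show that many subjects had more than 6. A reader might also infer that the tail is simply understated. For the shortest courses the error runs the other way: at LLOQ 0.05 the 6 × 300 mg figure is 7.5 months longer than the figure for 2 injections.

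**Conclusion.** The point holds as a cheap improvement to an exploratory output; it is not an error in the plan. Under Table 1's variances, the 95th percentile of time above LLOQ for 300 mg spans about 12.5 months between 2 and 24 injections (30 to 42.5 at LLOQ 0.05). From 6 to 24 injections the gain is about 5 to 5.5 months for 300 mg and 2 to 2.5 months for 300/100 mg, and medians move by about 0.5 month or less.

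The direction is secure as long as release is slow and variable between subjects. The number of months is less so. Table 1 is the earlier model, and by Protocol Section 1.3 the studies behind it did not follow PK beyond 2 months after the last injection. The simulations will use the refined model, whose structure may be revised (SAP Section 13.2.4.1). The LLOQ and the longer course lengths are my assumptions.

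**What to change.** In SAP Section 13.2.6, keep the 6-injection course of each regimen as the reference. Commit to the same simulations at the minimum, median and maximum number of injections that enrolled subjects actually received. These counts can be taken from the dosing information already going into the NONMEM file. Beside every time-above-LLOQ percentile and every monthly percentage below LLOQ, state the treatment length to which it applies.

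The cost is a short change to the SAP, a few extra runs of the same final model and the tables that go with them. No new data or subjects are needed. The sponsor would have to report longer upper-tail durations for longer courses and shorter ones for the shortest. This concerns simulation scenarios only and says nothing about how patients should be dosed.

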#### **14. INTERIM ANALYSIS**

No formal interim analysis is pre-specified for the study. However, during the course of the study, data relevant to PK analysis will be summarized and reviewed to facilitate decision making regarding potential modification of study duration.

## 15. DETERMINATION OF SAMPLE SIZE

The sample size is based on practical considerations and no statistical power is calculated. Approximately 60 subjects will be enrolled in Part A. This number of subjects is expected to provide a reasonable description of the distribution of plasma and urine concentration data in the overall population over the timeframe investigated (i.e., 12 to 36 months post the last SUBLOCADE injection), given the low-moderate interindividual variability (~30%) observed for SUBLOCADE PK in previous studies. The number of subjects to be enrolled in Part A is also limited by the availability of patients who received at least 2 SC injections of SUBLOCADE in Phase III studies and who remain in the time window targeted for enrolment in the current study. A maximum of 30 Part A subjects will proceed to Part B; it is anticipated that approximately 30 subjects will be sufficient to address the objectives for Part B. The final number of subjects will depend on results from quantitative buprenorphine UDS in Part A. Data will be reviewed on an ongoing basis.

## **16. COMPUTER METHODS**

Statistical analyses will be performed using version 9.4 (or newer) of SAS on a Windows operating system.

The non-linear mixed-effects modeling software NONMEM version 7.3.0 or older (ICON plc, Gaithersburg, MD) will be used for the population PK analysis. The stochastic approximation expectation-maximization (SAEM) with interaction computational algorithm will be used for model estimation. Standard errors at the final model parameter estimates will be calculated subsequently using the importance sampling approach (IMP) as implemented in NONMEM. Perl-speaks-NONMEM (PsN, version 4.6.0) will be used to operate NONMEM. Dataset preparation, exploratory analyses, processing of model outputs and model simulations will be performed using R software version 3.4.3 or older.

## 17. CHANGES TO ANALYSES SPECIFIED IN PROTOCOL

The definition for Full Analysis Set was rephrased to be clearer:

### **Definition in the Protocol:**

All subjects enrolled in Part A will be included in the Full Analysis Set – Part A and all subjects enrolled in Part B will be included in the Full Analysis Set – Part B. The Full Analysis Set consists of all subjects who received at least 2 SC doses of SUBLOCADE in Study RB-US-13-0003 or both Studies RB-US-13-0003 and INDV-6000-301 and was enrolled in the current study. This will be the analysis population for all analyses.

### **Definition in the SAP:**

**FAS Part A:** The FAS Part A consists of all subjects who are screen success and who have at least one measure of buprenorphine or norbuprenorphine concentration in plasma or at least one measure of buprenorphine or norbuprenorphine concentration in urine (as free drug or from quantitative UDS) or at least one measure for buprenorphine qualitative UDS in Part A (from Scheduled or Unscheduled visits).

**FAS Part B:** The FAS Part B consists of all subjects who met continuation criteria for Part B and who have at least one measure of buprenorphine or norbuprenorphine concentration in plasma or at least one measure of buprenorphine or norbuprenorphine concentration in urine (as free drug or from quantitative UDS) or at least one measure for buprenorphine qualitative UDS in Part B (from Scheduled or Unscheduled visits).

The **FAS** consists of all subjects who are part of FAS Part A and/or FAS Part B.

19. APPENDIX

APPENDIX 1: SCHEDULE OF EVENTS

	Screening	Part A	END OF PART A Subjects can proceed into Part B only if they meet continuation criteria b	Part B	
Visit		Visit 1 a		Visit 2	Visit 3 a
Day	Day 1 c	Day 1 c		30 days from Visit 1 ±7 days	30 days from Visit 2 ±7 days
Visit Window					
Informed Consent	X				
Demographics	X				
Eligibility Criteria	X				
Body Weight		X			
Height		X			
Body Mass Index (calculated in eCRF)		X			
Medical History d		X			
Urine Sample e		X	X	X	
Urine Pregnancy Test f		X	X	X	
Blood (PK) Sample		X	X	X	
Adverse Events g		X	X	X	
Concomitant Medications h		X	X	X	
Buprenorphine Question i			X	X	

eCRF=electronic case report form; PK=pharmacokinetic

a Visit 1 acts as the End of Study visit for Part A and Visit 3 acts as the End of Study visit for Part B. If a subject experiences the onset of a serious adverse event assessed by the Investigator as related to study procedures within a period of 30 days following study completion or withdrawal, and the Investigator will follow the procedures defined in Section 10 and Section 11 of the study protocol for assessing, documenting, and reporting these events.

b Subjects who achieve negative results for both buprenorphine and norbuprenorphine quantitative UDS (irrespective of naloxone result) at Visit 1 will conclude their study participation, as will subjects who achieve a positive result for buprenorphine and/or norbuprenorphine and a positive result for naloxone on the quantitative UDS performed at Visit 1. Subjects who achieve a positive result for buprenorphine and/or norbuprenorphine

and a negative result for naloxone on the quantitative UDS performed at Visit 1 can continue into Part B of the study if Part B is still open to enrolment.

c The Screening visit becomes Visit 1 for subjects eligible to enter Part A (that is, those that are not screen failures).

d Medical history since end of previous participation in Phase III SUBLOCADE study.

e From the urine sample collected, 2 aliquots will be sent to the bioanalytical laboratory and 1 aliquot will be sent to the diagnostic laboratory, and if applicable, the remaining urine will be used for a dipstick pregnancy test.

f Urine pregnancy tests will be performed for any woman of childbearing potential (defined as all women who were not surgically sterile or postmenopausal for at least 1 year prior to informed consent). Pregnancy is not exclusionary for enrolment and pregnancy during the study does not lead to discontinuation.

g Only adverse events and serious adverse events related to study procedures and/or study conduct should be collected in the eCRF.

h Concomitant medications are all medications taken during the study, including any prescribed medication-assisted treatment (methadone, naltrexone, buprenorphine), and will be captured. Of note, any extended-release buprenorphine treatment initiation will lead to study discontinuation.

i Ask about the subject's illicit buprenorphine use in the last 14 days. If the subject has used prescribed and not illicit buprenorphine, capture in Concomitant Medications. Illicit use will not impact the subject's participation on the study.

## APPENDIX 2: PARTIAL DATE IMPUTATION

### Missing Severity in Adverse Events

If the severity is missing for an AE, then a severity of “Severe” will be assigned.

The imputed values for assessment will be used for incidence summary, while the actual values will be presented in data listings.

### Missing Date Information for Adverse Events

When the AE start date is incomplete (i.e., partially missing), then the following rules will be applied:

#### Missing day and month

- If the year is the same as the year of the date of the first visit date in Part A, then the day and month of the date of the first visit date in Part A will be assigned to the missing fields.
- If the year is before the year of the first visit date in Part A, then December 31 will be assigned to the missing fields.
- If the year is after the year of the date of the first visit date in Part A, then January 1 will be assigned to the missing fields.

#### Missing month only

- The day will be treated as missing and both month and day will be replaced according to the above procedure.

#### Missing day only

- If the month and year are the same as the month and year of the first visit date in Part A, then the day of the first visit date in Part A will be assigned to the missing day.
- If either the year is before the year of the date of the first visit date in Part A or if both years are the same but the month is before the month of the first visit date in Part A, then the last day of the month will be assigned to the missing day.
- If either the year is after the year of the date of the first visit date in Part A or if both years are the same but the month is after the month of the date of the first visit date in Part A, then the first day of the month will be assigned to the missing day.

If the start date is after the stop date after missing value calculation, the stop date will be used as the start date.

### **Missing Date Information for Concomitant Medications**

For concomitant medications, incomplete (i.e., partial missing) start date and/or stop date will be imputed. When the start date and the stop date are both incomplete for a subject, consider imputing the start date first.

#### **Missing day and month**

- If the year of the incomplete start date is the same as the year of the date of the first visit date in Part A, then the day and month of the date of the first visit in Part A will be assigned to the missing fields.
- If the year of the incomplete start date is before the year of the date of the first visit date in Part A, then December 31 will be assigned to the missing fields.
- If the year of the incomplete start date is after the year of the date of the first visit date in Part A, then January 1 will be assigned to the missing fields.

#### **Missing month only**

- The day will be treated as missing and both month and day will be replaced according to the above procedure.

#### **Missing day only**

- If the month and year of the incomplete start date are the same as the month and year of the first visit date in Part A, then the day of the first visit date in Part A will be assigned to the missing day.
- If either the year is before the year of the first visit date in Part A or if both years are the same but the month is before the month of the first visit date in Part A, then the last day of the month will be assigned to the missing day.
- If either the year is after the year of the date of the first visit date in Part A or if both years are the same but the month is after the month of the first visit date in Part A, then the first day of the month will be assigned to the missing day.

